### 7.2.2 Exclusion Criteria

1. Patient with pathologic variations of the *ABCB11* gene that predict complete absence of the BSEP protein
2. Patient with past medical history or ongoing presence of other types of liver disease including, but not limited to, the following:
  - a) Biliary atresia of any kind
  - b) Benign recurrent intrahepatic cholestasis, indicated by any history of normal s-BAs
  - c) Suspected or proven liver cancer or metastasis to the liver on imaging studies
  - d) Histopathology on liver biopsy is suggestive of alternate non-PFIC related etiology of cholestasis
3. Patient with a past medical history or ongoing presence of any other disease or condition known to interfere with the absorption, distribution, metabolism (specifically bile acid metabolism), or excretion of drugs in the intestine, including but not limited to, inflammatory bowel disease

4. Patient with past medical history or ongoing chronic (i.e., >3 months) diarrhea requiring intravenous fluid or nutritional intervention for treatment of the diarrhea and/or its sequelae
5. Patient has a confirmed past diagnosis of infection with human immunodeficiency virus or other present and active, clinically significant, acute, or chronic infection, or past medical history of any major episode of infection requiring hospitalization or treatment with parenteral anti-infective treatment within 4 weeks of treatment start (study Day 1) or completion of oral anti-infective treatment within 2 weeks prior to start of Screening Period
6. Any patient with suspected or confirmed cancers except for basal cell carcinoma, and non-liver cancers treated at least 5 years prior to Screening with no evidence of recurrence
7. Patient with a past medical history of chronic kidney disease with an impaired renal function and a glomerular filtration rate  $<70 \text{ mL/min/1.73 m}^2$
8. Patient with surgical history of disruption of the enterohepatic circulation (biliary diversion surgery) within 6 months prior to start of Screening Period.
9. Patient has had a liver transplant or a liver transplant is planned within 6 months of randomization
10. Decompensated liver disease, coagulopathy, history or presence of clinically significant ascites, variceal hemorrhage, and/or encephalopathy
11. INR  $>1.4$  (the patient may be treated with Vitamin K intravenously, and if INR is  $\leq 1.4$  at resampling the patient may be randomized)
12. Serum ALT  $>10 \times$  upper limit of normal (ULN) at Screening
13. Serum ALT  $>15 \times$  ULN at any time point during the last 6 months unless an alternate etiology was confirmed for the elevation
14. Total bilirubin  $>10 \times$  ULN at Screening
15. Patient suffers from uncontrolled, recalcitrant pruritic condition other than PFIC. Examples include, but not limited to, refractory atopic dermatitis or other primary pruritic skin diseases
16. Any patient who is pregnant or lactating or who is planning to become pregnant within 24 weeks of randomization
17. Sexually active males and females who are not using a reliable contraceptive method with  $\leq 1\%$  failure rate (such as hormonal contraception, intrauterine device, or complete abstinence) throughout the duration of the study and 90 days thereafter (from signed

informed consent through 90 days after last dose of study drug). See [Appendix 6](#) for further details

18. Patient with a past medical history of alcohol or substance abuse will be excluded. Patient must agree to refrain from illicit drug and alcohol use during the study
19. Administration of bile acid or lipid binding resins and medications that slow GI motility (Refer to [Appendix 1](#) – Concomitant Medications Guidelines)
20. Patient has had investigational exposure to a drug, biologic agent, or medical device within 30 days prior to Screening, or 5 half-lives of the study agent, whichever is longer
21. Patient who has been previously treated with an IBAT inhibitor whose pruritus has not responded to treatment
22. Any other conditions or abnormalities which, in the opinion of the investigator or Medical Monitor, may compromise the safety of the patient, or interfere with the patient participating in or completing the study

### **7.2.3 Withdrawal of Patients**

Patients/caregivers will be informed that they have the right to withdraw from the study at any time, without prejudice to their medical care, and that they are not obliged to state their reasons.

Any withdrawal, and reasons for withdrawal, must be fully documented in the electronic case report form (eCRF) and source documents and the patient followed by the investigator/investigative staff. Even after the study is completed at the Follow-up Visit, the investigator/investigative staff will, regardless of reason for withdrawal, record any patient data they receive concerning SAEs, and all drug-related non-serious AEs, and subsequently report these according to Section 10.1. Withdrawn patients will not be replaced.

Patients will be withdrawn in the following circumstances:

- A patient's/caregiver's desire for withdrawal for any reason
- Lost to follow-up (every effort must be made to contact the patient/caregiver; a certified letter must be sent)
- An AE that, in the opinion of the investigator, necessitates withdrawal
- A worsening of the symptoms related to diarrhea occurs
- Death
- Patient/caregiver estimation of intolerable symptoms
- A patient's/caregiver's substantial noncompliance (eDiary and study drug compliance) or protocol violation

- An investigator's opinion that continuing the patient in the study is not appropriate. The investigator may withdraw a patient at any time, if it is considered to be in the patient's best interest

A patient who withdraws from treatment prematurely will have EOT (Visit 9) assessments at the time of withdrawal and a follow-up assessment (Visit 10) 28 days following the last dose of study drug, and the patient will be recorded as withdrawn.

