### **5.3.1 Risk/Benefit**

A4250 has been evaluated in three Albireo-sponsored clinical studies: a double-blind placebo-controlled study in healthy volunteers, a single-dose ADME study, and a Phase 2 study in children with cholestatic pruritus. In addition, an investigator-sponsored study has been conducted in patients with PBC.

Healthy subjects have been exposed to up to 10 mg as a single dose and up to 3 mg daily as part of a multiple-dose evaluation. Children with cholestatic liver disease have been treated with up to 0.2 mg/kg/day (200 µg/kg/day) for 4 weeks. In total, 2 SAEs have been reported; both were judged by the physician to be not related to the study drug.

Patients with cholestatic liver diseases suffer from excess bile acids in the liver resulting in tissue damage. A commonly used treatment in these patients is bile diversion surgery, whereby approximately 50% to 100% of the enterohepatic circulation of bile acids is interrupted. Inhibition of IBAT with A4250, thereby interrupting the enterohepatic circulation of bile acids, is therefore a potential medical alternative to surgery which could be of benefit to these patients if shown to be effective and safe. Data from the Phase 2 study showed efficacy of A4250 in reducing s-BA concentrations and pruritus in such patients.

Based on the mode of action of an IBAT inhibitor, loose stools or diarrhea could be expected. However, in the pediatric Phase 2 study with 4 weeks daily treatment, only one patient had mild transient diarrhea after a single dose that did not recur on multiple dosing.

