## 7 INVESTIGATIONAL PLAN

### 7.1 Overall Study Design and Plan

#### 7.1.1 Description

This is a double-blind, randomized, placebo-controlled, Phase 3 study to investigate the efficacy and safety of 40 µg/kg/day and 120 µg/kg/day of A4250 compared to placebo in children with PFIC (deficiencies of FIC1 or BSEP).

Study data will be periodically (approximately on a quarterly basis) reviewed by an unblinded Data Safety and Monitoring Board (DSMB).

The study includes a 35- to 56-day Screening Period followed by a 24-week Treatment Period and a 4-week Follow-Up Period.

After completion of the Screening Period, eligible patients (20 per treatment group) will be randomized on Day 0 (Visit 3) in a 1:1:1 fashion to receive 40 µg/kg/day or 120 µg/kg/day of A4250, or a matching placebo.

Patients who complete the Treatment Period and Visit 9 (Day 168) in this study will be invited to participate in a 72-week open-label extension study (A4250-008; EudraCT Number 2017-002325-38, subject to a separate study approval) in which all patients will receive active treatment.

Visit windows applicable to each visit are presented in the schedule of assessments ([Table 1](#)). There will be up to 10 clinic visits during the study ([Figure 1](#)) and one scheduled telephone contact, as follows:

- Visit 1: Screening Period start. Patient is considered enrolled after signing the informed consent form (ICF) (Days -56 to -35)
- Visit 2: second Screening Visit (Days -28 to -7)
- Visit 3: Randomization Visit (Day 0)
- Telephone Contact 1: (Day 14)
- Visit 4: Clinic Visit (Day 28)
- Visit 5: Clinic Visit (Day 56)
- Visit 6: Clinic Visit (Day 84)
- Visit 7: Clinic Visit (Day 126)
- Visit 8: Clinic Visit (Day 154)
- Visit 9: Clinic Visit, End of Treatment ([EOT] Day 168)
- Visit 10: Follow-Up Visit, 28 days after last dose of study drug (Day 196). All patients continuing in Study A4250-008 will not have this Follow-up Visit.

Additional clinic visits may be required for patients who need direct site assistance, e.g., due to AE monitoring, to fulfil screening requirements, and/or for safety maintenance.

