#### **10.2.2.4 Diarrhea**

Study drug should be discontinued if a patient develops diarrhea with at least 1 of the following concomitant signs or symptoms: grossly bloody stools, vomiting, dehydration requiring treatment with oral or intravenous rehydration and/or electrolyte imbalances, fever ( $\geq 38$  C) and/or the diarrhea persists for 7 or more days.

If there is gross blood in stool, INR and platelets should be measured.

Study drug will be reintroduced (re-challenge) when the symptoms have resolved. If the diarrhea re-occurs within 1 week after the re-challenge with no alternate etiology, the patient will be permanently discontinued and monitored as outlined in [Section 10.2.2.5](#).

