#### **10.2.2.5 Monitoring after Permanent Discontinuation of Study Drug Due to Safety**

Once study drug is permanently discontinued for liver, hepatitis, diarrhea, or other severe AE related to study drug, the patient will be monitored weekly until the laboratory and clinical parameters have normalized/stabilized.

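### For a child whose diarrhea worsens to a Section 10.2.2.4 trigger and then resolves, Section 7.2.3 requires withdrawal and Section 10.2.2.4 requires re-challenge

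*Protocol*

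**What the plan says.** Three parts of the current protocol (24 June 2019) bear on a child with diarrhea on study drug.

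- **Section 7.2.3, Withdrawal of Patients.** The list opens "Patients will be withdrawn in the following circumstances", and one bullet reads "A worsening of the symptoms related to diarrhea occurs". The bullet names no severity, duration or recurrence and does not refer to Section 10.2.2.4. The bullet on adverse events in the same list does leave the decision to the investigator. The section also states "Withdrawn patients will not be replaced". A withdrawn patient has the end-of-treatment assessments and is recorded as withdrawn.
- **Section 10.2.2.4, Diarrhea.** Drug is stopped for diarrhea accompanied by a listed sign (gross blood, vomiting, dehydration needing treatment and/or electrolyte imbalance, fever) or lasting 7 days or more. Then: "Study drug will be reintroduced (re-challenge) when the symptoms have resolved". The permanent stop comes later: "If the diarrhea re-occurs within 1 week after the re-challenge with no alternate etiology, the patient will be permanently discontinued".
- **Section 10.2.2.5** describes monitoring "Once study drug is permanently discontinued for liver, hepatitis, diarrhea, or other severe AE related to study drug".

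Section 5.3.1 says of the mechanism: "Based on the mode of action of an IBAT inhibitor, loose stools or diarrhea could be expected". The versions of 01 March 2019 and 29 April 2019 carry the same pair of rules.

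**The concern.** Both rules are mandatory, and for some children they require opposite actions. A withdrawn child cannot be re-challenged, so a site cannot follow both. Neither section refers to the other, and no precedence rule appears in the protocol as shown.

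The event in question is the side effect the protocol expects from the mechanism. Withdrawal therefore takes out children whom the dedicated diarrhea section would put back on drug, and it would more plausibly do so in the active arms. Section 11.2.2.2 sets the price. A dropout is a non-responder on the bile acid endpoint, and planned pruritus assessments after premature treatment discontinuation are negative, with all 336 kept in the denominator. The effect would be dilution of the treatment difference and unclear instructions to sites.

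**Working it through.** **1. Where the two rules meet.**

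| Course of the diarrhea | Section 7.2.3 | Section 10.2.2.4 | Result |
|---|---|---|---|
| New onset, presents with a listed sign, then resolves | Need not be a worsening | Stop, then re-challenge | No conflict |
| Present, worsens, stays below the triggers | Withdraw | Silent | 7.2.3 over-broad, no contradiction |
| Present, worsens to a trigger, then resolves | Withdraw | Stop, then re-challenge | Conflict |
| Recurs within 1 week of re-challenge, no other cause | Withdraw, if read as a worsening | Permanent discontinuation | No conflict |

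The contradiction is confined to the third row.

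**2. The plan's own power.** Inputs from Section 11.1: 20 per arm, 60% responders on active, 10% on placebo, one-sided 0.025, pooled doses tested first and then each dose. For each comparison I used the unstratified CMH statistic Z = (x − E)/√V, where x is the number of active responders, m all responders, N = n₁ + n₂, E = n₁m/N and V = n₁n₂m(N − m)/[N²(N − 1)]. A dose succeeds if Z ≥ 1.96 both for the pooled comparison and for that dose. Enumerating every outcome gives 94.9% for a particular arm, 98.3% for at least one and 91.5% for both. The protocol states approximately 94%, 99% and 91%, so its figures are reproduced.

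**3. Illustration of the cost.** Assumption: exactly one child per affected arm is withdrawn under Section 7.2.3 although Section 10.2.2.4 would have restarted drug. That child is a certain non-responder; the others respond at the planned rates.

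| Scenario | Per arm | Particular active arm | Both active arms |
|---|---|---|---|
| No such child | 20 | 94.9% | 91.5% |
| One in each active arm | 20 | 92.7% | 88.1% |
| One in a single active arm | 20 | 92.8% (that arm) | 89.8% |
| One in every arm, placebo included | 20 | 93.5% | 89.3% |
| One in each active arm | 22 | 94.4% | 90.6% |
| One in each active arm | 23 | 95.6% | 92.4% |

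At 20 per arm the loss is 94.9 − 92.7 = 2.2 points for a particular arm. A stratified CMH simulation agrees on size: 93.9% to 91.7% for a particular arm and 89.8% to 86.4% for both. It used 20,000 runs and assumed strata per arm of 6/6/5 PFIC-2 and 1/1/1 PFIC-1 by age; the stratum-pooling rule was not applied. The 22 and 23 rows correspond to 66 and 69 patients, inside the 60 to 70 planned in Section 11.1.

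**4. Pruritus.** Planned assessments: 168 days × 2 = 336. Withdrawal at Day 84 makes (168 − 84) × 2 = 168 of them negative, which is half. No pruritus power was computed.

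**The case against.** The strongest defence is that this is one loose bullet and that a sensible site would follow the detailed diarrhea section. The word worsening could mean failure after re-challenge. It could also mean worsening of diarrhea present at entry, since exclusion criterion 4 bars only chronic diarrhea that needed intravenous fluid or nutritional intervention. Either reading would remove or narrow the clash. Both are plausible intentions, but Section 7.2.3 states neither, so the ambiguity stands.

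Four stronger readings might be inferred and are not supported:

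- **Every diarrhea stop is contradictory.** It is not; the table above shows how narrow the overlap is.
- **Section 10.2.2.5 settles the matter for Section 10.2.2.4.** It covers what follows permanent discontinuation and does not say how that point was reached, so it favors neither section.
- **A withdrawn child is barred from the extension.** Section 7.1.1 says "Patients who complete the Treatment Period and Visit 9 (Day 168) in this study will be invited to participate". It does not say that nobody else may enter, and the extension protocol is not shown. The 29 April 2019 text did offer entry to patients who withdrew for intolerable symptoms after at least 12 weeks, and the current text does not. Loss of access is therefore a fair inference but no more than that.
- **The power loss is an estimate of what will happen.** The only clinical figure at hand is from the pediatric Phase 2 study: one patient with mild, transient diarrhea after a single dose, among 20 patients treated for 4 weeks. Nothing shows that this case met a Section 10.2.2.4 trigger. The study was short, so it does not rule such cases out, but it supplies no rate.

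The enrollment margin also counts for the plan: if it is used, it absorbs the illustrated loss. Repetition of the same text in the two earlier 2019 versions shows that the wording is not new in the last amendment, but it adds no separate evidence of conflict.

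**Conclusion.** The point holds in a limited form and is minor. Sections 7.2.3 and 10.2.2.4 give opposite mandatory instructions for a child whose existing diarrhea worsens to a Section 10.2.2.4 trigger and then resolves. Below the triggers, the Section 7.2.3 bullet is broader than it needs to be, without contradicting anything.

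The certain consequences for a child withdrawn this way are no replacement, non-response on bile acids, and negative pruritus assessments from then on. The size cannot be derived from the protocol. Under the assumption of one such child per active arm, the cost is about 2 points of per-arm bile acid power at exactly 20 per arm, and per-arm power would stay at about 94% to 96% with 22 to 23 per arm. If these withdrawals fall mainly on the active arms, the direction is dilution; this does not point to a false positive result.

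**What to change.** Replace the diarrhea bullet in Section 7.2.3 with: *diarrhea requiring permanent discontinuation per Section 10.2.2.4*. If the medical team prefers a different threshold, state that one rule identically in both sections; the threshold is a clinical choice. Keep the other Section 7.2.3 bullets (investigator-judged adverse event, intolerable symptoms, investigator opinion), so that a child who should come off study for diarrhea short of that rule still can.

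Cost: one bullet reworded at the next amendment and a short memo to sites. No change to the analysis, endpoints or sample size is needed.

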#### **7.2.4 Study Termination by Sponsor**

This study may be terminated at any time by Albireo if serious side effects should occur, if the investigator does not adhere to the protocol; or if, in the sponsor's judgment, there are no further benefits to be achieved from the study. In this event, Albireo/designee will inform the study investigators, institutions, and all regulatory authorities.

Albireo may temporarily or permanently discontinue the study at an investigative site at any time for safety, ethical, compliance, or other reasons. If this is necessary, Albireo will endeavor to provide advance notification to the site. If a site or the study is suspended or discontinued, the investigator/investigative staff will be responsible for promptly informing the Independent Ethics Committee (IEC). If required by local regulations, Albireo/designee will be responsible for informing the IEC and the regulatory authority of study or site discontinuation. In such an event, all study data and unused study drug must be returned to Albireo.

## 8 TREATMENT OF PATIENTS

### 8.1 Identity of Study Drug

A4250 and placebo will be supplied as capsules for oral administration. White opaque capsules filled with pellets containing A4250 or placebo will be provided. Two different capsule sizes will be available, as follows:

- Capsule size 0 that can be opened
- Capsule size 3 that should be swallowed intact. These size 3 capsules may be opened only under exceptional circumstances, e.g., patient cannot swallow capsule intact

The content of the A4250 and placebo capsules will be identical in appearance. Capsule filling weight will also be identical for high dose, low dose, and placebo. Bottles with 34 capsules will be given to the patient at each visit. A patient who requires 2 or more capsules per day will be given multiple bottles. Refer to the investigational product manual.

### 8.2 Administration of Study Drug

Patients will be dosed with A4250 at a dose of 40 µg/kg/day, 120 µg/kg/day, or placebo for 24 weeks. Study drug will be dispensed to the patient at Visits 3, 4, 5, 6, 7, and 8, together with instructions on how to store and take the drug. Study drug administration data, including whether each patient took each dose or partial doses of study drug, whether there were any delayed or missed doses, and whether the capsule was opened or swallowed whole will be documented through the eDiary and transferred to the study database.

A4250 should be taken in the morning, together with food. On clinic visits days when laboratory assessments are conducted, study drug should be taken after the visit and after laboratory samples are taken. Patients should not crush or chew the capsule(s). When swallowing the capsule intact, the patient should administer the dose with a glass of water.

For a patient unable to swallow capsule intact, the capsule can be opened and the contents sprinkled and mixed in a small amount of soft room-temperature yogurt, apple sauce, or fruit purée. A list of food options can be found in the Pharmacy manual. The amount of food should be less than what the patient/infant is expected to eat and should be followed by water.

1. Hold the capsule over the prepared food, gently twist open and allow the content to fall into food
2. Mix the entire capsule content with 1 or 2 tablespoons (15 to 30 mL) of soft food (apple sauce, fruit purée, or yogurt)
3. Administer the mixture immediately after mixing.

The number of capsules provided to the patient will be based on body weight at Visit 3. At Visit 6, if a patient's weight has shifted to another weight category (identified in [Table 2](#)), the number of capsules per day may be adjusted.

**Table 2 Dosing and Capsule Strength**

Body Weight (kg)	Capsule Size	Number of Capsules per Day	Capsule Strength, Low Dose (µg)	Total Dose (µg)	Capsule Strength, High Dose (µg)	Total Dose (µg)	Capsule Size, Placebo (µg)
5.0 to <7.5	0	1	200	200	600	600	0
7.5 to <12.5	0	2	200	400	600	1200	0
12.5 to <17.5	0	3	200	600	600	1800	0
17.5 to <19.5	0	4	200	800	600	2400	0
19.5 to <25.5	3	2	400	800	1200	2400	3
25.5 to <35.5	3	3	400	1200	1200	3600	3
35.5 to <45.5	3	4	400	1600	1200	4800	3
45.5 to 55.5	3	5	400	2000	1200	6000	3
>55.5	3	6	400	2400	1200	7200	3

### 8.3 Study Treatment Packaging and Labeling

#### 8.3.1 Packaging and Labeling

The capsules will be packed in high-density polyethylene containers, with child-proof polypropylene caps. Study drug capsules containing A4250 in the strength specified in [Table 2](#) above will be manufactured.

Packaging and labeling will be prepared to comply with applicable regulatory requirements.

